#### **6.4.2.2 Secondary Non-Clinical Endpoints**

Serum samples will be collected at baseline and week 12 prior to patch placement for analysis of inflammatory cells and markers. Additionally skin and serum

samples will be collected for analysis of inflammatory cells and markers 72 hours after patch placement at baseline and week 12. We will also collect one additional biopsy from an area of persistent, chronic dermatitis if present after the 10-week course of dupilumab. Skin biopsies will be collected at 72 hours after patch testing from the sites of allergen placement and will be initially placed in saline. Blood samples will also be collected on the same day. DNA and RNA will be isolated from PBMCs and 300 um of tissue. The isolated DNA will be subjected to TCR HTS of the TCRB gene before and after therapy. We will determine the CDR3 sequence of the top 5 most prevalent clones in the skin of patch tested skin before therapy, which likely represents at least one of the pathogenic T cell clones specific to the allergen. We will quantify the presence and abundance of those same clones in the blood and patch tested skin after therapy as a measure of T cell trafficking (ie ability of those same T cell clones being able to reenter skin at site of specific allergen placement may be inhibited after dupilumab therapy). The RNA will be subjected to multiplex gene expression analysis of 594 human immune genes to specifically characterize the Th1, Th2, Th17, and Th22 skewing of the immune microenvironment as well as quantify the expression of alarmins and proteases known to be important in the elicitation phase of allergic contact dermatitis. These gene signatures and immune cell subtypes analyses will be confirmed at the protein level with multispectral immunofluorescence on the skin and flow cytometry in the blood.

Novel Technologies to be used: High throughput sequencing of the T cell receptor CDR3 region (TCR HTS) is a powerful technology that measures the CDR3 sequences and the relative frequencies of all T cells in a biologic specimen, allowing study of individual T cell clones as well as studies of the entire T cell population in a patch tested skin lesion. Tyramide signaling amplification immunostaining/multi-spectral imaging and automated image analysis. This technology provides visualization of up to 6 proteins of interest for state-of-the-art phenotypic and functional analyses compared to standard IHC. Tyramide signaling amplification (TSA) allows for sequential immunostaining of the same tissue section for up to six different markers. We will utilize the revolutionary Perkin-Elmer Mantra Quantitative Pathology Imaging Microscope which scans each slide and extracts the data from each individual fluorescence channel so that each marker can be displayed in separate images. This imaging technology allows the equivalent of flow cytometry profiling on tissue sections and it works particularly well on FFPE samples, as shown below in Preliminary Studies. NanoString-based technologies. NanoString-based gene expression analysis using their human immunology panel allows robust and direct quantification of 594 mRNA sequences in FFPE tissues, allowing quantitative gene profiling studies utilizing our skin biopsy specimens. This panel allows for immune cell subset analysis of Th1, Th2, Th17 and Th22 cells by using a subset of genes whose expression is largely specific to certain immune cell populations. The underlying assumption from this

model is that these characteristic genes are expressed only in that cell type and are expressed at the same level in each cell (these are essentially reference genes specific to individual cell types). Under this model, a cell type's abundance can be measured as the average logscale expression of its characteristic genes that are concordant within the sample. This allows an unbiased comparison of relative abundance of cell types between sample groups. It also allows for comparisons between cell types.

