## PROTOCOL SYNOPSIS

Protocol Title:	The Effects of Dupilumab on Allergic Contact Dermatitis
Site Numbers & Names:	001 Brigham and Women’s Hospital, Department of Dermatology
Research Hypothesis:	Dupilumab will most likely benefit patients who have persistent allergic contact dermatitis to allergens that primarily elicit a Th2 immune response (ie rubber and fragrance) but may also benefit patients who have sensitivities to allergens that primarily elicit Th1, Th17 and Th22 immune responses (ie nickel).
Study Schema: Drugs / Doses / Length of Treatment)	Dupilumab 300 mg/2mL; 7 doses; 10 weeks of treatment
Study Objectives: 
 
• Primary:
 
• Secondary:
 
	
 
• Primary endpoint 1: Number of patients who achieve a reduction in patch test site reactions from 2+–3+ at baseline to “?” or no reaction at week 12.
 
• Secondary endpoint 1: Number of patients who achieve a reduction in investigator global assessment (IGA; IGA = vIGA-AD) from 3 or greater at screen and baseline to 0 or 1 at Week 6 and at Week 12.
 
• Secondary endpoint 2a: To quantify the inflammatory markers (Th1, Th2, Th17, Th22 immune pathways) in the blood and skin of patients before and after dupilumab. Secondary endpoint 2b: Changes in IGA from baseline to week 12. Other secondary endpoints: Change in baseline eczema-area-and-severity-index (EASI), body surface area (BSA), numerical rating scale (NRS) itch, dermatology life quality index (DLQI), and SLEEPYQ from baseline to Week 6 and Week 12.
 
• Secondary endpoint 3: Changes in IGA from baseline to Week 6 and to Week 12.
 
• Secondary endpoint 4: To identify and quantify the top T cell clones by T-cell receptor high-throughput sequencing in the skin and blood before therapy and quantify their abundance after therapy.
 
• Other secondary endpoints: Change in baseline eczema-area-and-severity- index (EASI), body surface area (BSA), numerical rating scale (NRS) itch, dermatology life quality index (DLQI), and SLEEPYQ from baseline to Week 6 and to 12.
 

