and Th17-related gene expression in the skin of patients with atopic dermatitis. Therefore, we hypothesize that dupilumab will most likely benefit patients who have persistent allergic contact dermatitis to allergens that primarily elicit a Th2 immune response (ie rubber and fragrance), but may also benefit patients who have sensitivities to allergens that primarily elicit Th1, Th17, and Th22 immune responses (ie nickel). We propose to test this hypothesis by treating patients who have failed allergen avoidance and skin directed therapy with dupilumab and monitoring their responses in the following ways before and after therapy: using well-established clinical parameters addressing skin inflammation and quality of life issues, assessing whether the most abundant T cell clones (defined as the top 5 most abundant clones present in the skin at patch test site before therapy) can still traffic to the skin after therapy, and quantifying the changes in the inflammatory Th1, Th2, Th17 and Th22-specific immune gene signatures before and after treatment.

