### **2.2 Secondary Objectives**

Secondary endpoint 1: Number of patients who achieve a reduction in investigator global assessment (IGA) from 3 or greater at screen and baseline to 0 or 1 at Week 6 and Week 12.

Secondary endpoint 2a: To quantify the inflammatory markers (Th1, Th2, Th17, Th22 immune pathways) in the blood and skin of patients before and after dupilumab. Using novel nanostring-based gene expression assays and multispectral immunofluorescence we will quantify changes in key genes that are specific for the Th1, Th2, Th17, Th22 immune pathways in the skin and blood of patients before and after treatment with dupilumab. Secondary endpoint 2b: Changes in IGA from baseline to week 12. Other secondary endpoints: Change in baseline eczema-area-and-severity-index (EASI), body surface area (BSA), numerical rating scale (NRS) itch, dermatology life quality index (DLQI), and SLEEPYQ from baseline to Week 6 and Week 12.

Secondary endpoint 3: To measure the reductions in the severity of clinical skin disease and quality of life scores with dupilumab treatment. We will measure changes in investigator global assessment (IGA; scored on a scale of 0-5 with 0 being no disease and 5 being the most severe disease) from baseline to Week 6 and Week 12.

Secondary endpoint 4: To address whether dupilumab affects T cell trafficking, use high-throughput sequencing of the T-cell receptor (TCR HTS) to identify the unique

CDR3 sequence of the likely pathogenic T cell clones before therapy and quantify their relative frequency in the skin after dupilumab therapy.

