We will recruit 30 patients with allergic contact dermatitis 18 years of age and older up to 6 months after patch testing with a documented IGA of at least 3 at baseline and screening visits, and at least one 2+ (strong) or 3+ (extreme) reaction on patch testing to participate in this open-label pilot study. If more than one 2+ (strong) or 3+ (extreme) reactions are present, up to two may be selected for evaluation in the study. Priority will be given to nickel, fragrance mix I or II, and rubber as these allergens have been studied previously with respect to their preferential T helper cell skewing. At the initial screening visit, demographic information will be obtained, inclusion and exclusion criteria as detailed in Section 4.2 will be reviewed, and informed consent obtained for those deemed eligible for enrollment. A single subcutaneous dose of 600 mg will be self-administered at week 0 +72-120 hours and 300 mg every 2 weeks thereafter for a total 10 weeks of therapy. Subjects will be evaluated for improvement in primary and secondary endpoints using clinical examination and questionnaires during initial and follow-up visits at Week 0, Week 6, and Week 12 as per Time and Events Schedule. Patch test site reactions will also be evaluated 72 hours after the Week 0 and Week 12 visits. Skin biopsies will be taken at these two time points from both the patch test site reaction and from normal skin taken from a non-dermatitic area on the contralateral side of the body. For the Week 12 patch placement, a site contralateral to the Week 0 patch placement site will be chosen. If an area of persistent dermatitis other than the patch test site(s) is also present at week 12+72-120 hours an additional biopsy will be taken unless in an anatomic location not amenable to biopsy (face, hands, elbows, knees, genitals, feet). Serum samples will be obtained at four time-points including Week 0 (prior to patch placement), Week 0 +72-120 hours, Week 12 (prior to patch placement), and Week 12 +72-120 hours. If subjects do not mount a 2+ (strong) or 3+ extreme reaction to the tested allergens at the Week 0 +72-120 hour visit they will be discontinued from the study and will not receive dupilumab. These patients will be considered screen fails. Week 10 +72-120 hours will conclude the end of the treatment portion of the study. Week 12 +72-120 hours will conclude the subjects' participation in the study.

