### **6.4.2 Secondary Efficacy Assessments**

#### **6.4.2.1 Secondary Clinical Endpoints**

Secondary endpoint 1: Number of patients who achieve a reduction in investigator global assessment (IGA) from 3 or greater at screen and baseline to 0 or 1 at Week 6, and Week 12.

Secondary endpoint 2a: To quantify the inflammatory markers (Th1, Th2, Th17, Th22 immune pathways) in the blood and skin of patients before and after dupilumab. Secondary endpoint 2b: Changes in IGA from baseline to week 12. Other secondary endpoints: Change in baseline eczema-area-and-severity-index (EASI), body surface area (BSA), numerical rating scale (NRS) itch, dermatology life quality index (DLQI), and SLEEPYQ from baseline to Week 6 and Week 12.

Secondary endpoint 3: Changes in IGA from baseline to Week 6 and Week 12.

Other secondary endpoints: Change in baseline eczema-area-and-severity-index (EASI), body surface area (BSA), numerical rating scale (NRS) itch, dermatology life quality index (DLQI), and SLEEPYQ from baseline to Week 6 and Week 12.

Secondary endpoint 4: Identification and quantification of the most prevalent T cell clones in the skin before therapy and how those clones change after therapy using high-throughput sequencing of the TCRB gene.

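### Secondary endpoint 4 ranks its five T-cell clones in the same pre-therapy biopsy that supplies their baseline, so their skin abundance tends to fall by Week 12 even with no drug effect

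*Combined protocol and SAP*

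**What the plan says.** Section 6.4.2.2 fixes the selection rule: "We will determine the CDR3 sequence of the top 5 most prevalent clones in the skin of patch tested skin before therapy". Section 1.2 gives the same rule, "defined as the top 5 most abundant clones present in the skin at patch test site before therapy". The follow-up measurement is also in 6.4.2.2: "We will quantify the presence and abundance of those same clones in the blood and patch tested skin after therapy". Its stated purpose is to measure T-cell trafficking, on the idea that the "ability of those same T cell clones being able to reenter skin at site of specific allergen placement may be inhibited after dupilumab therapy".

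Section 6.4.2.1 words the endpoint as a change, covering "the most prevalent T cell clones in the skin before therapy and how those clones change after therapy". Section 2.2 makes the measure a relative frequency: "CDR3 sequence of the likely pathogenic T cell clones before therapy and quantify their relative frequency in the skin after dupilumab therapy".

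The schedule in Section 6.1 has skin samples at two times only, Week 0 +72-120 hours and Week 12 +72-120 hours. Section 4.1 describes a patch-site biopsy and a normal-skin biopsy at each, with up to two allergens per patient, and adds: "For the Week 12 patch placement, a site contralateral to the Week 0 patch placement site will be chosen". Section 9.4.3 divides the skin between freezing and culture, not between ranking and measurement, and names no analysis for this endpoint.

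The synopsis differs on where clones are ranked. It speaks of the "top T cell clones by T-cell receptor high-throughput sequencing in the skin and blood before therapy and quantify their abundance after therapy".

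**The concern.** The clones that rank highest in one noisy sample are partly those that are truly abundant and partly those that happened to be over-represented there. Measured again in a fresh sample, the second component does not recur, so the selected group comes back lower. This is regression to the mean, caused by selecting on the same measurement that serves as baseline. Placing the Week 12 patch on the opposite side adds site-to-site variation, which enlarges the effect.

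At stake is the reading of one mechanistic secondary endpoint. A fall in top-five skin abundance would look like support for inhibited re-entry, when part or all of it could come from how the clones were chosen. The study has no control arm in which the same artefact would appear and could be compared.

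**Working it through.** **The plan's own figure.** The documents give no figure for this endpoint. The only calculation, in Section 9.1, concerns patch test reactions. It reproduces: a one-sample t-test needs n = 10 for a change of -1.0 with SD 1.0; 10 x pi/3 = 10.5, rounded up to 11; simulated power of the signed-rank test at 11 is 0.81; and 11/(1 - 0.20) = 13.75, rounded up to 14. It is used below only for the number of patients, 14.

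**One sample, two uses.** That the baseline comes from the ranking biopsy is inferred from Sections 4.1 and 6.1: no other pre-therapy patch-site skin is taken, and no replicate is described.

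**Direction.** Let X1 and X2 be clone frequencies in the Week 0 and Week 12 biopsies, and S1 and S2 their respective top-five sets. By definition of S2, the sum of X2 over S1 is at most the sum of X2 over S2. If the biopsies are exchangeable, the sum of X2 over S2 has the same distribution as the sum of X1 over S1. Hence E[Week 12 abundance of S1] <= E[Week 0 abundance of S1], strictly so unless the Week 0 top five always rank as the top five at Week 12. No distribution for clone sizes is needed.

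**Size.** This rests on assumptions, since the documents give none of the inputs. Assumed: 2,000 clones with log-normal frequencies, independent log-normal site noise, 5,000 templates per biopsy, no drug effect, no time trend. The fall is 1 minus the Week 12/Week 0 ratio of summed top-five frequency, averaged on the log scale.

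| Clone log SD | Site log SD 0 | 0.25 | 0.5 | 1.0 | Week 0 top-five share |
|---|---|---|---|---|---|
| 1.0 | 9% | 21% | 45% | 82% | 4-8% |
| 1.5 | 3% | 11% | 29% | 70% | 9-15% |
| 2.0 | 1% | 7% | 20% | 58% | 19-26% |
| 2.5 | 0.5% | 4% | 14% | 48% | 33-38% |

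At 20,000 templates with no site variation the fall is 0.1-2.5%. A separate simulation with Zipf and log-normal clone sizes and 500 to 10,000 cells gave a fall in all 27 settings, from 0.1% to 75%. When the baseline instead came from an independent pre-therapy sample, the expected change was zero (for example 0.0290 against 0.0289).

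**Offset.** If the true top five are boosted by 0.5 log at Week 12 (site log SD 0.5), the ratio is 0.74 / 0.99 / 1.09 for clone log SD 1.0 / 1.5 / 2.0. Boosting can cancel the fall.

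**Presence.** With 5,000 templates at both visits, about 95-100% of the selected clones are still detected at Week 12. With 500 templates at Week 12 it is about 91%.

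**Blood.** With ranking in skin only, the blood ratio is 0.999-1.001.

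**Reverse look-up** (Week 12 top five at Week 0). Under exchangeability it agrees with the forward ratio within 0.02. It moves when something else differs:
- True top five down 1.0 log, site log SD 0.25: reverse 0.72 / 0.99 / 1.21 for clone log SD 1.0 / 1.5 / 2.0, against 0.79 / 0.90 / 0.94 with no effect.
- Clone replacement (top five down 1.5 log, next five up 1.5 log): forward 0.43-0.63, reverse 0.23-0.28.
- No effect, site log SD 0.5 at Week 0 but 0.25 at Week 12: forward 0.56-0.82, reverse 0.78-0.92.

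**Illustration only.** The plan names no test here. If a signed-rank test were applied to 14 patients, a fall would be declared under no effect in 0.06 to 1.00 of trials across the table's settings, against a nominal 0.025 in that direction.

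**The case against.** The case on the other side has several parts.

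*This is an uncontrolled pilot, the wording is tentative, and no before/after fall could establish a drug effect anyway.* True, and it limits the severity. But selection bias is a separate problem from the missing control: it shifts a purely descriptive before/after figure too, in the direction of the hypothesis.

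*The size could be negligible.* It could, if a few clones dominate and sampling is deep and uniform. Nothing in the documents shows that this will be so. A reader might infer that the observed Week 0 top-five share would settle it. It does not, because the share mixes clone spread with site noise: in the assumed model a share of about 8% goes with an 82% fall, and one of about 9% with a fall of 2-3%.

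*Presence is closest to the question whether clones can still reach the skin, and it is nearly unaffected.* This stands when sampling is deep, so the point is limited to abundance.

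*The source of the counts is unsettled.* Section 6.4.2.2 takes DNA from tissue, while 9.4.3 sends one portion of skin to culture for T-cell isolation and then lists TCR sequencing. This also stands. It adds to the uncertainty about size, not about direction.

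*The reverse look-up has limited diagnostic value.* Agreed. A reader might take it as the size of the selection effect, to be subtracted from the forward fall. The figures above rule that out. The visits are also unequal by design: Sections 4.1 and 4.2.1 require a 2+ or 3+ reaction at Week 0, with no such condition at Week 12, so tissue yield and noise may well differ.

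**Conclusion.** The concern holds for the abundance of the selected clones in patch-tested skin. Under exchangeability the direction is a matter of logic. The size is unknown: about 0.1% to 82% under the assumed values, with nothing in the documents to narrow it.

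Stronger readings are not supported. A reader might infer that a fall is certain or must be an artefact. It is neither: the Week 0 patch is itself an allergen challenge and could boost the clones, and a real effect may be present as well. A reader might extend the bias to blood. Under 6.4.2.2 blood plays no part in selection; only if the synopsis wording means ranking in blood too would blood be affected in the same way. A reader might also conclude that the plan will declare a false significant result, but no test is named for this endpoint.

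This is a cheap improvement worth making, confined to one secondary endpoint. The primary endpoint and the sample size are untouched.

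**What to change.** In Sections 6.4.2.2 and 9.4.3:

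1. State that a fall in the abundance of the Week 0 top five is not by itself evidence of inhibited re-entry, because selecting on the baseline sample produces a fall, and that without a control arm no change can be attributed to the drug.
2. Report the forward look-up (Week 0 top five at Week 12) at full depth and at equal template depth. Beside it, report the reverse look-up at equal depth, descriptively. Use it only to ask whether the data are compatible with no change: similar forward and reverse falls are what selection alone would give. Do not subtract one from the other.
3. Report presence at Week 12 alongside abundance, with the Week 12 template count.
4. Make the synopsis agree with 6.4.2.2 on where the clones are ranked.

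The cost is a little more analysis and a more cautious conclusion, with no new sample or visit. Equalising depth discards reads and can enlarge the forward fall: with a 500-template Week 12 sample, clone log SD 1.0 and site log SD 0.25, the ratio goes from 0.78 at full depth to 0.42. The equal-depth forward figure should therefore be read only beside the reverse at that depth.

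Two alternatives are less attractive. A separate pre-therapy biopsy used only for ranking would remove the effect (ratio 0.97-1.00) but adds a procedure. Splitting the templates of the one Week 0 biopsy removes only the sequencing part (ratio 1.00 with no site variation, but 0.19-0.53 at site log SD 1.0).

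### The NanoString cell-type score does not support comparing levels between cell types, so Th1/Th2/Th17/Th22 skewing should be defined on changes

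*Combined protocol and SAP*

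**What the plan says.** Section 6.4.2.2 plans multiplex RNA analysis of 594 immune genes in order "to specifically characterize the Th1, Th2, Th17, and Th22 skewing of the immune microenvironment". Skewing is not defined there or elsewhere.

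The technology paragraphs of the same section give the scoring model. The underlying assumption of the "model is that these characteristic genes are expressed only in that cell type and are expressed at the same level in each cell". A type's abundance is then taken as "the average logscale expression of its characteristic genes that are concordant within the sample". Two uses follow. The first is "This allows an unbiased comparison of relative abundance of cell types between sample groups". The second is the sentence at issue: "It also allows for comparisons between cell types". No condition is attached to it.

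Section 6.4.2.1 frames secondary endpoint 2a as quantifying the pathway markers "in the blood and skin of patients before and after dupilumab". Section 6.4.2.2 adds that the gene signatures and cell-subtype analyses "will be confirmed at the protein level with multispectral immunofluorescence on the skin and flow cytometry in the blood". Section 9.4.3 lists the endpoint but gives no analysis for it.

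**The concern.** The first use compares one cell type with itself in different samples. The second compares different cell types, which are measured by different genes. The assumption of equal expression in each cell fixes a given gene's level across cells of its type. It does not make the levels of different genes equal. The plan gives no calibration and does not assume that the constants are equal across types.

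This matters because Section 6.4.2.2 is the only description of how the scores will be compared, and the most direct reading of skewing is one type relative to another. An analyst following the text could rank Th2 above Th1 in a biopsy on score levels and cite the protocol for it. That ranking would partly reflect which genes happened to represent each type.

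**Working it through.** There is no stated figure to reproduce. The check is algebra on the plan's own model, followed by an illustration on assumed inputs.

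**Model.** For characteristic gene g of type k in sample i, on the log2 scale: log x(g,i) = c(g) + log a(k,i). Here a(k,i) is the abundance of type k and c(g) is a constant for the gene. Averaging over the genes of type k gives the score S(k,i) = C(k) + log a(k,i), where C(k) is the mean of the c(g).

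**Same type, two samples.** S(k,i) − S(k,j) = log[a(k,i)/a(k,j)]. C(k) cancels, so the plan's first use holds.

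**Two types, one sample.** S(k,i) − S(l,i) = log[a(k,i)/a(l,i)] + [C(k) − C(l)]. The last bracket remains. It is the same in every sample, so averaging over patients does not shrink it.

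**Worked example (assumed values).** Mean constants are 9 for Th1 and 11 for Th2. Abundance falls from 100 to 80 for Th1 and from 50 to 20 for Th2.

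| | Th1 score | Th2 score | Th2 − Th1, score | Th2 − Th1, true |
|---|---|---|---|---|
| Before | 9 + 6.64 = 15.64 | 11 + 5.64 = 16.64 | +1.0 | log2(50/100) = −1.0 |
| After | 9 + 6.32 = 15.32 | 11 + 4.32 = 15.32 | 0.0 | log2(20/80) = −2.0 |
| Change | −0.32 | −1.32 | −1.0 | −1.0 |

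Both level comparisons are off by 11 − 9 = 2. Before treatment the order is reversed. The within-type changes, and the difference between them, are exact.

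**Possible size.** The documents give neither the spread of the constants nor the number of genes per type. Assume independent normal constants with SD s (log2) and m genes per type. The offset then has SD s√(2/m). A true 2-fold difference (1 log2 unit) is ranked wrongly with probability Φ(−1/[s√(2/m)]), taken over possible gene sets, not over patients.

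| s | m | SD of offset (log2) | As a fold difference | Wrong order |
|---|---|---|---|---|
| 0.5 | 5 | 0.32 | 1.2 | 0.1% |
| 1 | 5 | 0.63 | 1.5 | 5.7% |
| 2 | 5 | 1.26 | 2.4 | 22% |
| 3 | 5 | 1.90 | 3.7 | 30% |
| 2 | 1 | 2.83 | 7.1 | 36% |
| 2 | 10 | 0.89 | 1.9 | 13% |

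For s = 3 and m = 5: 3 × √0.4 = 1.90, 1/1.90 = 0.53, Φ(−0.53) = 0.30.

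**Gene list.** The plan averages genes that are concordant within the sample. If that selection were made sample by sample and a gene set fell from a genes to b, the score would shift by an amount with SD s√(1/b − 1/a). With s = 2, going from 5 genes to 4 gives 2 × √(1/4 − 1/5) = 0.45 log2, or 1.36-fold. Going from 5 to 3 gives 0.73, or 1.66-fold. This is conditional: the plan does not say that the selection is made that way.

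**The case against.** The strongest reply is that no planned analysis uses the disputed comparison. The sentence closes a description of what the platform can do. Sections 1.2, 2.2 and 6.4.2.1 all describe pathway changes before and after treatment, and no endpoint ranks one type against another. The sentence also has a valid reading: coming straight after the remark on sample groups, it could mean comparing those group differences across types. Finally, protein-level confirmation is planned.

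Much of this stands. A reader might infer that endpoint 2a is invalid; as a before/after contrast within a type, on a fixed gene set, it is sound under the model. A reader might also infer that the trial's hypothesis depends on finding which pathway dominates. It does not: Section 1.4 concerns which patients benefit, and Section 1.2 takes the allergens' T-helper profiles as already known.

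It does not dispose of the point. The text does not limit itself to the valid reading, skewing is undefined, and no other section says how scores will be compared. Immunofluorescence and flow cytometry could inform between-type abundance directly, but they are planned as confirmation and do not make the score comparable across types.

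**Conclusion.** The between-type claim is wrong for score levels within a sample. That follows from the stated model and needs no outside figure. It holds unless the mean constants are equal across types, which the plan does not assume.

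The size of the error is unknown. The 0.1% to 30% range for a 2-fold difference rests entirely on an assumed SD of 0.5 to 3 log2 and 5 genes per type; with few genes and a wide spread it is higher.

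Two stronger readings are not supported. The first is that score levels are uninformative about relative abundance. They are offset: at SD 2 with 5 genes, a 2-fold difference is still ordered correctly in 78% of gene-set draws. The second is that the gene set will differ between visits. The wording on concordance leaves that possible but does not state it, and if the model held exactly, a type's genes would move together and none would be discordant.

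**What to change.** In Section 6.4.2.2, delete the sentence, or restrict it to comparing changes, or differences between sample groups, across cell types. Define skewing on that scale, for example (Th2 at Week 12 minus Th2 at Week 0) minus (Th1 at Week 12 minus Th1 at Week 0), using the biopsies taken after patch placement at each time. A contrast between allergen groups can be built the same way, since the constants cancel there too.

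As a precaution, fix one gene list per pathway before any Week 12 sample is analysed and apply it to every sample. Concordance then cannot alter the list between visits.

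No assay, sample or visit changes. The price is a narrower claim: the score will show which pathway changed more, not which cell type is more abundant. If between-type abundance is wanted, it should be drawn from the immunofluorescence and flow cytometry, and the plan should say so.
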